## 6.1.3 Adverse Event Severity

The Investigator will assess the Grade of the AE per the NCI-CTCAE v5.0 or higher (Appendix 2). Toxicities that are not specified in the NCI-CTCAE will be defined as follows:

- Grade 1: Mild; asymptomatic or mild symptoms; clinical or diagnostic observations only; intervention not indicated
- Grade 2: Moderate; minimal, local, or noninvasive intervention indicated; limiting age-appropriate instrumental activities of daily living (ADL)
- Grade 3: Severe or medically significant but not immediately life-threatening; hospitalization or prolongation of hospitalization indicated; disabling; limiting self-care ADL
- Grade 4: Life-threatening consequences; urgent intervention indicated
- Grade 5: Death related to AE

#### 6.1.4 Serious Adverse Event (SAE)

An SAE is any untoward medical occurrence that at any dose:

- results in death
- is immediately life-threatening
- requires inpatient hospitalization or prolongation of existing hospitalization

- Elective or pre-planned treatment for a pre-existing condition that is unrelated to the indication under study and has not worsened since signing the ICF (documented as medical history on the eCRF) is not considered an SAE.
- Scheduled therapy for the target disease of the study, including admissions for transfusion support or convenience, is not considered an SAE.
- results in persistent or significant disability/incapacity
- results in congenital anomaly/birth defect
- is considered an important medical event
  - If an AE does not meet 1 of the serious criteria, but the Investigator or Sponsor considers an event to be clinically important, the event could be classified as an SAE under the criterion of an "Important Medical Event." Examples of such medical events may include allergic bronchospasm requiring intensive treatment in an emergency room or at home, or blood dyscrasias or convulsions that do not result in in patient hospitalization.

## 6.1.5 AE Relationship to Study Medication

The Investigator must assess whether the AE may be related to ANK-700 (study drug) or any protocol mandated procedure, when applicable. The relationship is defined below:

Relationship assessments that indicate the event is "Not Drug Related":

- Not Related
- Unlikely Related

Relationship assessments that indicate the event is "Drug Related":

- Possibly Related
- Related

#### **6.1.6** Dose-Limiting Toxicity (DLT)

Dose-limiting toxicities for Study ANK-700-01 include any Grade 2 AE not resolving within 14 days or any ≥ Grade 3 AE occurring during the dose-escalation safety monitoring period (D1 to D15 in Part A; D1 to D22 in Part B). DLTs do not include those AEs attributable solely to intercurrent illness or other concomitant medications. Any DLT experienced during the dose-escalation safety monitoring period will result in study pause and review by the SMC.

Any  $\geq$  Grade 4 AE will result in notification to the Food and Drug Administration (FDA) in parallel with the SMC; all study dosing and enrollment will be paused pending review by FDA.

## **6.1.7 Clinical Laboratory Endpoints**

The following laboratory parameters will be measured at screening and at the time points specified in the Schedule of Assessments and will be analyzed locally by a certified laboratory:

- A serum pregnancy test during screening for all women of child-bearing potential (WCBP)
- Serum or Urine testing for all WCBP prior to each dose
- Hematology laboratory parameters include white blood cell (WBC) count, hemoglobin, hematocrit, platelet count, and WBC differential
- Blood chemistry laboratory parameters, including blood urea nitrogen, creatinine, glucose, AST, ALT, ALP, bilirubin (total and direct), electrolytes (sodium, chloride, bicarbonate, potassium), amylase, lipase, albumin, magnesium, calcium, and phosphorus
- Coagulation laboratory parameters, including prothrombin time, partial thromboplastin time or activated partial thromboplastin time, and international normalized ratio
- Complete urinalysis with qualitative analysis for protein (dipstick)
- HIV, HBV (hepatitis B surface antigen, hepatitis B core antibody, and hepatitis B surface antibody), and HCV (hepatitis C) testing (screening only)

#### 6.1.8 Expanded Disability Status Scale (EDSS)

The EDSS is based on a standard neurological examination, incorporating the pyramidal, cerebellar, brainstem, sensory, bowel/bladder, visual, and cerebral [or mental] functional systems, and ambulation, rated and scored as functional system scores. The EDSS is a disability scale that ranges in 0.5-point steps from 0 (normal) to 10 (death). See Appendix 3 for score details.

#### 6.1.9 Brain Magnetic Resonance Imaging

Screening and post dose brain MRIs will be performed. Scans will be performed by trained and certified MRI technicians. The MRI will include the acquisition of scans at each time point with and without IV administered gadolinium contrast enhancement.

The following time windows apply:

- "Screening/baseline" MRI should be performed on or after the Screening Visit, but ≥ 10 days before the D1 visit.
- The MRI obtained for the Part A D15 Visit and Part B D22 Visit should be performed up to 3 days before or on the scheduled visit day.
- MRI at Part B visit D90 should be performed within 2 weeks of the scheduled visit.

MRIs will be performed for assessment of safety only and will be reviewed locally. Data collected for each MRI will include number of FLAIR lesions, number of enhancing lesions, and presence of restricted diffusion. For post-baseline scans there will be an assessment of whether there was improvement or worsening from prior scans.

If a relapse occurs at the time of a scheduled MRI, the MRI should be obtained before initiation of corticosteroid therapy or the MRI should be postponed by 1 month.

All patients with new neurological symptoms suggestive of MS relapse should have an MRI performed (which may include the spinal column) during an unscheduled visit, if clinically necessary, but before the initiation of steroids.

## 6.1.10 Other Safety Assessments (Physical Exam, Vital Signs and ECG)

The Physical exam will include an assessment of general appearance, skin, head, neck, throat, lymph nodes, cardiovascular, neurological, thyroid, musculoskeletal/extremities, respiratory, abdomen, height, and weight (baseline only).

Vital signs will include temperature, pulse rate, and systolic and diastolic blood pressure (sitting for 5 minutes). If vital signs need to be repeated during a single visit, assessments should be conducted approximately 5 minutes apart.

At screening, a standard 12-lead electrocardiogram (ECG) will be obtained at baseline and interpreted by the Investigator to confirm eligibility.

Any new clinically significant (CS) abnormality from baseline should be recorded as an AE.

#### **6.2** Pharmacokinetic Assessments

Blood samples will be collected for measurement of ANK-700 as specified in Appendix 1 Table 1 (Part A), Table 2 (Part B, Cohort 4) and Table 3 (Part B, Cohort 5). The timing of sampling may be altered based on the emerging PK data. The adjustment of the PK sampling schedule is not considered to be a substantial amendment so long as the total number of plasma PK samples and the total blood volume to be collected from each participant will not change. Any adjusted sampling time points will be documented appropriately.

PK parameters of ANK-700 will be determined from the plasma concentration-time data. Parameters will be calculated by non-compartmental modeling methods, using actual elapsed time from start of infusion based on the actual mg administered. The parameters that will be calculated are defined in the table below and will be calculated for single or multiple dosing of ANK-700, as appropriate. Not all listed parameters may be calculable for every patient, and additional parameters may be calculated, if needed, to fully characterize the available data. PK parameters and concentration data will be summarized by Part, by Dose, and by Day (Single dose Day 1, Multiple dose Day 1, Multiple dose Day 4, Multiple dose Day 7, Single and Multiple Dose Day 1 for common doses.

Table 1 Pharmacokinetic Parameters for Part A and Part B After Each Dose

Parameter	Definition	Method of Determination
C max	Maximum observed plasma concentration	Obtained directly from the concentration-time data
T max	Time to first occurrence of $C_{max}$	Obtained directly from the concentration-time data
$\lambda_{\rm z}$	Terminal elimination rate constant	Terminal phase rate constant calculated by linear regression of the log-linear concentration-time curve. Only those data points judged to describe the terminal log-linear decline will be used in the regression. A minimum number of three data points in the terminal phase will be used in calculating $\lambda_z$ with the line of regression starting at any post- $C_{max}$ data point ( $C_{max}$ should not be part of the regression slope) and including $C_{last}$ , $t_{last}$ . The adjusted correlation coefficient ( $R^2$ adjusted) in general should be greater than 0.90. Any value less than 0.90 may be used at the PK Scientist's best knowledge and judgment. An appropriate number of decimal places should be used for $\lambda_z$ to enable the reported value of $t_{1/2}$ to be calculated.
t 1/2	Terminal elimination half-life	$Log_e(2)/\lambda_z$
AUC last	Area under the plasma concentration-time curve from time 0 to the last measurable time point	The linear-log trapezoidal method will be employed to calculate AUCs. The linear method will be used for all incremental trapezoids arising from increasing concentrations and the logarithmic trapezoidal method will be used for those arising from decreasing concentrations. $AUC_t = \int_0^t \mathbf{C}(\mathbf{t}) d\mathbf{t}.$
AUC inf	AUC from time zero extrapolated to infinity	$AUC_{inf} = \int_0^t \mathbf{C}(\mathbf{t}) d\mathbf{t} + \int_{\mathbf{t}}^{\infty} \mathbf{C}(\mathbf{t}) d\mathbf{t} =$ $AUC_t + C_t / \lambda_{z_m} \text{ where } C_t \text{ is last observed quantifiable}$
		concentration.
%AUC ex	Percentage of AUC (0-inf) obtained by extrapolation	$(1 - [AUC_t/AUC_{inf}]) \times 100$
CL	Clearance	dose/AUC inf
V z	Volume of distribution during terminal phase	$CL/F/\lambda_z$
R acc ,AUC	Accumulation ratio based on AUC	
$R_{acc}, C_{max}$	Accumulation ratio based on Cmax	
$C_{trough}$	Predose plasma concentration	

For cohort by cohort PK analysis, not all PK parameters may be calculated, and non-compartmental analysis may be done using nominal times from start of infusion.

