#### 4.7. Dose Escalation Safety Monitoring Period

In Part A, the dose-escalation safety monitoring period is from the beginning of the IV administration of ANK-700 through the D15 clinic visit. Any AEs that meet the criteria defined in Section 4.6 but occur after the dose-escalation safety monitoring period of Part A, may be considered by the SMC in the evaluation for Part B dose selection.

The dose-escalation safety monitoring period in Part B is from the beginning of the first IV administration of ANK-700/PBO through the D22 clinic visit.

The monitoring period is supported by nonclinical animal data, which demonstrate:

- ANK-700 is cleared from circulation in < 7 minutes, ensuring that > 5 half-lives have elapsed during the safety monitoring period
- T-cell tolerance induction can be observed as early as 1 week after drug administration in nonclinical models, ensuring the mechanism of action will be active and robust during the safety monitoring period
- Immunologically active antigen cannot be detected in animals 7 days after GP-peptide administration, ensuring that any processed antigen will be cleared during the safety monitoring period

AEs and any abnormal clinical parameters, including laboratory findings, observed during this period will be used by the SMC to determine whether dose escalation should proceed.

No patient with a DLT will be replaced.

In both parts, patients will be monitored in the clinic for 8 hours after the completion the first IV administration of ANK-700/PBO. In Part B, patients will be monitored in the clinic for 4 hours after completion of their second and third dose.

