## 2.3.2 PART B: MAD (Multiple Ascending Doses)

The first MAD cohort (Cohort 4) will be initiated after the safety review of SAD Cohort 2 (Part A), a recommendation to proceed by the SMC, and approval by the Sponsor.

Patients in the MAD part will be randomized as described in Section 3.2. Patients will arrive at the clinic on the morning of dosing and will be monitored in-clinic for 24 hours after completion of their first infusion for assessment of acute safety and PK blood sample collection.

A total of 3 doses (1 dose every 3 days on D1, D4, and D7) will be administered in Part B, a regimen that was effective in animal models of MS. Patients will return to the clinic on D22, D43±2, and at 3, 6, and 12 months for follow-up.

Doses planned for evaluation in Part B include 0.3 mg/kg (Cohort 4) and 1.0 mg/kg (Cohort 5). Both Part B cohorts will employ sentinel dosing to monitor for the acute and subacute safety of multiple doses of ANK-700. In this design, the first 2 patients in each cohort (1 ANK-700 and 1 PBO) will complete all 3 doses and complete an additional 14 days of safety monitoring (through D21) before initiating dosing for any subsequent patients. Based upon the expected short half-life (< 7 minutes) of ANK-700, no accumulation is anticipated with multiple doses administered 3 days apart.

Initiation of Cohort 5 will only commence after review of the safety, tolerability, and laboratory test and available PK data of all the SAD cohorts (Cohorts 1 to 3) and Cohort 4 through D22, recommendation by the SMC, and approval by the Sponsor.

For all patients in Part B, the study will consist of a screening period of up to 28 days, followed by 3 doses of study drug, 1 dose administered on D1, D4, and D7. Blood and plasma samples will be collected for PK and ADA assessments during Part B of the study. In

the event that patients are unable to return to the clinic for protocol-specified visits, alternative methods for safety assessments and data collection may be employed to ensure the safety of the patients where appropriate.

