## 2.4 Study Drug Dosage and Administration

Administration of study drug in 100 mL normal saline will be by IV infusion over approximately 30 minutes.

For Part A, patients will receive a single IV infusion of ANK-700 only (i.e. no PBO). The following doses will be given:

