#### 10.3 Concentrations Below the Limit of Quantification (BLQ)

For PK data, all concentrations BLQ will be labeled as "BLQ" in the concentration data listings. Values that are BLQ will be substituted by for the calculation of descriptive statistics of concentration tables and for the individual and mean concentration-time plots.

For non-compartmental PK analysis, all below the limit of quantification (BLQ) values predose to the first dose, and prior to the first quantifiable concentration will be substituted by zeros. BLQ values between non-BLQ concentrations will be considered missing before the calculation of the PK variables. Terminal BLQ values will be considered missing.

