- ¹One PK sample will be taken pre\_dose (≥at least 5 min prior to infusion), with all subsequent PK samples taken after the end-of-infusion (EOI) at the following time points: EOI 0 (+2) min, EOI 7 (±2) min, EOI 15 (±2) min, EOI 30 (±5) min, EOI 1 h (±5 min), EOI 2 h (±5 min), EOI 3 h (±5 min), EOI 4 h (±5 min), EOI 6 h (±5 min), and EOI 8 h (±5 min). PK samples to be taken from the arm that did not receive the infusion. The exact date and time of each sample collection must be recorded for all collected samples.
- The prepared saline bag and infusion line should be weighed before and after administration. These weights should be recorded using any available scale with a precision to at least one tenth of a gram (0.1 grams). Both weight measurements should be conducted using the same scale to reduce variability.

Abbreviations : ADA = anti-drug antibodies; D=day; Early Term = early termination; ECG =	
electrocardiogram; EDSS = Expanded Disability Status Scale;	
h= hours; EOI = end of infusion; HBV = hepatitis B virus; HCV = hepatitis C virus;	
min = minute; MRI = magnetic resonance imaging;	; PE
= physical examination; PK = pharmacokinetics; SAD = single ascending dose.	

Table 2: Schedule of Assessments Part B (MAD) COHORT 4 ONLY

Assessments	Screening	ng Treatment Period			Study Period					Early Term.
Study Day	-28 to 0	1	4	7	22	43±2	90±7	182±7	365±14	
Screening Assessment			1						ı	I
Informed consent	X									
Medical	37									
history/demographics	X									
Disease history	X									
Inclusion/exclusion	X									
ECG	X									
HIV, HBV, HCV										
testing	X									
Clinical Procedures			1			I	1	1		
Physical examination	X									X
Pregnancy test	X	$X^{f_{\bullet}}$	$X^{f,g}$	$X^{f, g}$						
Vital signs	X	Xg			X					
Concomitant										
medications and	X	X	X	X	X	X	X	X	X	X
procedures										
EDSS	X	Xg			Χ		X	X	X	
Safety Assessments			1						ı	I
Adverse events		X	X	X	X	X	X	X	X	X
Laboratory tests	V	379	379	379	37					v
(safety)	X	$X^{g}$	$X^{g}$	$X^{g}$	X					X
MRI i	X				X		X			
Study Drug Administr	ation		•	•			•		•	•
Randomization		X								
ANK-700 or PBO		$X^{,q}$	V.0	X o,q						
administration		$\Lambda^{\prime\prime}$	Λ΄	Λ						
Additional Blood Sam	ples									
PK blood sample		X	$X^{g}$	X	X					
ADA samples		$X^{g}$			X		X	X	X	X

<sup>a All patients should be contacted by site staff 1 day before each study visit for assessment of COVID-19 signs and symptoms.

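### One isolated quantifiable value after a run of BLQ samples can carry AUClast across the whole run; the clear case is the Part A Day 4 sample

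*SAP*

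**What the plan says.** **Rules.** SAP 6.2 Table 1 defines AUClast as the "Area under the plasma concentration-time curve from time 0 to the last measurable time point" and states that "the logarithmic trapezoidal method will be used for those arising from decreasing concentrations". For non-compartmental analysis (NCA), SAP 10.3 says that "BLQ values between non-BLQ concentrations will be considered missing before the calculation of the PK variables" and that "Terminal BLQ values will be considered missing". Neither section has a rule for a quantifiable value that follows several BLQ samples.

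**Acceptance criteria.** SAP 8.10.2 keeps a parameter out of the summaries, subject to the PK scientist's judgement, if adjusted r² is below 0.90, the terminal span is under 1.3 half-lives, or extrapolation exceeds 30%. This applies to the lambda-z-dependent parameters: lambda z, AUCinf, CL and Vz. AUClast is not among them, yet the same section uses it in the box plots for dose proportionality.

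**Schedule.** SAP 2.3.2 refers to the "expected short half-life (< 7 minutes) of ANK-700". SAP 2.4 gives the drug "by IV infusion over approximately 30 minutes". In SAP Appendix 1 Table 1 the first post-infusion samples are at "EOI 0 (+2) min, EOI 7 (±2) min, EOI 15 (±2) min, EOI 30 (±5) min", followed by 1, 2, 3, 4, 6 and 8 h and one more PK sample on D4±1. In Part B the D4 sample is taken before the second dose, the D7 series stops 4 h after the infusion, and one sample follows on D22.

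**Other source.** Protocol 12.8 leaves further NCA detail to a PK analysis plan, which is not among the documents.

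**The concern.** With so short a half-life, most of the scheduled profile should be BLQ. A run of BLQ samples at the end of a profile does no harm: it is dropped and AUClast stops at the last quantifiable value. If one later sample reads at the limit, through carry-over or assay noise for example, the same run becomes embedded. Its samples are still dropped, but AUClast now continues to the late reading, and a log trapezoid spans hours or days in which the drug was measured as not quantifiable.

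AUClast serves the secondary PK objective and the visual check of dose proportionality. Part A plans 3 patients per cohort, so one such patient can dominate a cohort's mean and spread. Without a stated rule, the decision to keep or drop the value would be made after seeing it.

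**Working it through.** The documents give no AUC, LLOQ or Cmax, so there is no planned figure to reproduce. The check applies the SAP's own rules to a simple profile.

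**Inputs from the documents**
- Infusion of 0.5 h (SAP 2.4).
- Nominal Part A sampling times (SAP Appendix 1 Table 1). D4 is taken as 72 h; the ±1 day window allows 48 to 96 h.
- Half-life below 7 min (SAP 2.3.2). Protocol 4.7 also says "ANK-700 is cleared from circulation in < 7 minutes, ensuring that > 5 half-lives have elapsed during the safety monitoring period". If clearance in 7 min is read as five half-lives, the half-life is 7/5 = 1.4 min. The range run is 1.4, 3, 5 and 7 min.
- 72 h at 7 min per half-life: 72 × 60 / 7 = 617 half-lives.

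**Assumptions**
- One-compartment decline, scaled to Cmax = 1 at end of infusion (EOI).
- Cmax/LLOQ of 10, 100, 1,000 or 10,000.
- One late value exactly at the LLOQ.

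**Formulas**
- Rising step: Δt × (C1 + C2)/2.
- Falling step: Δt × (C1 − C2)/ln(C1/C2).

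**Worked case: half-life 5 min, Cmax/LLOQ 100 (LLOQ = 0.01)**
1. Concentrations at EOI 0, 7, 15 and 30 min are 1, 0.379, 0.125 and 2⁻⁶ = 0.015625. At EOI 1 h the value is 2⁻¹² = 0.00024, so the six samples from 1 h to 8 h are BLQ.
2. AUClast without a late value: 0.250 + 0.075 + 0.030 + 0.013 = 0.368 Cmax·h.
3. Add a D4 value of 0.01. The six BLQ samples become missing, and the last step runs from 1.0 h (EOI 30 min) to 72 h: 71 × (0.015625 − 0.01)/ln(1.5625) = 71 × 0.005625/0.4463 = 0.895.
4. AUClast becomes 0.368 + 0.895 = 1.263, and 1.263/0.368 = 3.4.

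**Inflation of AUClast by one D4 value at the LLOQ (Part A)**

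| Cmax/LLOQ | 1.4 min | 3 min | 5 min | 7 min |
|---|---|---|---|---|
| 10 | 113 | 34 | 23 | 30 |
| 100 | 5.7 | 5.2 | 3.4 | 5.4 |
| 1,000 | 3.2 | 3.0 | 2.0 | 1.3 |
| 10,000 | 1.07 | 1.08 | 1.03 | 1.13 |

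AUClast at least doubles up to a ratio of about 380 to 1,700, depending on half-life. An isolated value at EOI 8 h instead gives 1.3- to 1.5-fold at a ratio of 100.

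**Effect on a cohort of 3 (one patient at 3.43-fold, the others equal)**
- Arithmetic mean: (1 + 1 + 3.43)/3 = 1.81-fold.
- Geometric mean: 3.43^(1/3) = 1.51-fold.

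**How often.** With an assumed isolated-positive rate f per sample and 9 Part A patients, the chance of at least one is 1 − (1 − f)⁹. This is 4.4% at f = 0.5%, 8.6% at 1% and 17% at 2%.

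**Do the acceptance criteria catch it?** In the D4 and D22 cases where lambda z could be fitted, adjusted r² was at most 0.77. AUCinf, CL and Vz would normally be withheld, while the inflated AUClast would be summarised.

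**Candidate rules**
- Ending the profile before the BLQ run gives a ratio of 1.00 in every case.
- Setting embedded BLQ values to zero but keeping the late value still gives 1.01- to 13.9-fold for D4, so that change alone is not enough.

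**The case against.** **The rule may exist elsewhere.** The PK analysis plan named in Protocol 12.8 is a natural place for it. This stands as a limit: one can say that the SAP lacks the rule, not that no document has it. But the SAP sets its own AUC and BLQ rules, states that it supersedes the protocol's statistical considerations, and does not point to that plan for BLQ handling.

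**The size is unknown.** This stands. With a sensitive assay (ratio 10,000) the D4 effect is only 3 to 13%. A reader might infer that a late value always multiplies AUC; the documents do not support that without a Cmax and an LLOQ.

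**Only part of the schedule is clearly exposed.** This stands too.
- A reader might infer that D22 is the worst case. At a ratio of 100 it would give 13- to 25-fold, but only if D22 were attached to the Day 7 profile. Nothing says so, and the Day 7 series is defined to 4 h after infusion.
- A reader might count all 25 planned ANK-700 patients (9 + 16) at D4 and obtain 22% at a 1% rate. In Part B that sample is the pre-dose trough of dose 2, so only the 9 Part A patients clearly count.
- A reader might infer false accumulation through R_acc,AUC. SAP Table 1 leaves that method blank, so which AUC enters the ratio is not established.

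**Harm is limited.** No hypothesis is tested, dose proportionality is judged informally from box plots, medians and geometric means are reported, and individual profiles would make a lone 72 h point visible. This lowers the stakes. It does not settle which AUClast belongs in the table.

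**A late value might be real.** The half-life figure rests on nonclinical data, and this is a first-in-human study. That is a fair reason to keep such values listed and to allow a sensitivity analysis.

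**Conclusion.** The gap is real and follows directly from the SAP's text: the AUClast end point, the log-down trapezoid and the embedded-BLQ rule together bridge a BLQ run whenever one later sample is quantifiable, and no criterion in the SAP stops this for AUClast.

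The supported case is Part A D4, in cohorts of about 3. The inflation ranges from a few percent to more than 100-fold across the assumed Cmax/LLOQ ratios. The 4 to 17% chance of occurrence rests on assumed isolated-positive rates. Effects through D22, the Part B D4 sample or R_acc,AUC are not established. For a secondary, descriptive endpoint this is worth correcting because it is cheap and is better settled before the data are seen.

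**What to change.** Add to SAP 6.2 Table 1 and SAP 10.3:
- After two consecutive post-infusion BLQ samples the profile ends for AUClast and lambda z; both use data up to the last quantifiable sample before them.
- Later quantifiable values are listed and flagged but not used in the primary NCA. If they recur across patients, a sensitivity AUClast that includes them is reported.
- A single embedded BLQ value stays missing.
- The Part B D4 pre-dose sample is the dose-2 trough, and the D22 sample is not part of the Day 7 profile.

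Align the PK analysis plan with this wording.

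The cost is SAP text only, with no change to sampling. The downside is that a genuine late reappearance of drug would not enter the primary AUC, though it would remain visible in the listings and plots.
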